3.1.2. Secondary Endpoints

Both Arms:

1. Proportion of subjects with “early response” at Day 5-7/Discharge (whichever is earlier), defined as a NIHSS drop of ≥ 10 points from baseline or NIHSS score 0 or 1
2. Proportion of subjects suffering all-cause mortality between the two groups.
3. Difference in median final infarct size at 24 (-6/+24) hours from randomization, by MRI T2/Flair or CT (if contraindicated for MR)
4. Proportion of revascularization rates at 24 (-6/+24) hours from randomization, by CT-MR core lab assessment of vessel patency on CTA/MRA.

Treatment Arm Only:

Analysis of vessel reperfusion rates (percentages) post device and post procedure, by angiography core lab measurement of modified TIC1 $\geq 2b$.

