Follow-Up Schedule	 All follow up time points are relative to time of randomization (time zero) with baseline data considered as data generated from time of index stroke admission and prior to randomization. 1. 24 (-6/+24) hours: MRI/MRA or CT/CTA (if MR is contra-indicated) and NIHSS assessment. Final infarct volume will be measured by MRI T2/Flair or CT (if MR is contraindicated). 2. Day 5-7 (if subject remains in hospital) or discharge, whichever is earlier: NIHSS and blinded mRS (Optional repeat MRI T2/Flair or CT, if MR is contraindicated, may be performed to assess infarct volume) 3. Day 30 (± 14): NIHSS and blinded mRS 4. Day 90 (± 14): NIHSS and blinded mRS 			
General Inclusion Criteria	 Clinical signs and symptoms consistent with the diagnosis of an acute ischemic stroke, and subject belongs to one of the following subgroups: Subject has failed IV t-PA therapy (defined as a confirmed persistent occlusion 60 min after administration) Subject is contraindicated for IV t-PA administration Age ≥18 Baseline NIHSS ≥10 (assessed within one hour of measuring core infarct volume) Subject can be randomized between 6 to 24 hours after time last known well No significant pre-stroke disability (pre-stroke mRS must be 0 or 1) Anticipated life expectancy of at least 6 months Subject or subject's Legally Authorized Representative (LAR) has signed the study Informed Consent form* * If approved by local ethics committee and country regulations, the investigator is allowed to enroll a patient utilizing emergency informed consent procedures if neither the patient nor the representative or person of trust is available to sign the informed consent form. However, as soon as possible, the patient is informed and his/her consent is requested for the possible continuation of this research. (Not applicable to U.S. Sites.) 			
General Inclusion Criteria (additional information)	 Subjects receiving heparin or low molecular weight (LMW) heparin e.g. Fragmin® (Dalteparin Sodium) or an intravenous direct thrombin inhibitor such as Angiomax® (Bivalirudin), or Argatroban within the last 24 hours from screening are eligible for participation if their coagulation profile remains acceptable. Subjects on factor Xa inhibitors (e.g. apixaban) or direct thrombin inhibitors are eligible for participation 			

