5.2.1 Justification for Expansion of Time Window

In the dynamic setting of ischemia, there is continuous growth of the infarct core at the expense of the penumbral tissue until either the infarct is completed or reperfusion is achieved. The pace of expanding cerebral ischemia is highly variable between individuals and is likely dependent on multiple factors, including the presence of collateral circulation, ischemic pre-conditioning, cerebral perfusion pressure, and cerebral blood volume as well as serum glucose, body temperature, and oxygen delivery capacity.

MRI perfusion and PET studies suggest that the time point at which half of the patients with large vessel stroke show evidence of persistent penumbra is between 8 to 12 hours. [66] One MRI perfusion study demonstrated that as many as 70-80% of the patients with proximal arterial occlusion may have a significant mismatch as far as 9 to 24 hours post stroke onset. [37] In a retrospective study of 75 patients with acute ischemic stroke treated with endovascular recanalization therapies beyond 8 hours after symptom onset (baseline NIHSS 14 ± 4.9 and time to treatment 15.2 ± 8.7 hours), revascularization resulted in reduced infarct growth. The infarct growth was significantly greater when the baseline volume of infarct tissue was small and revascularization was not achieved. [67] Another retrospective study of patients selected by CT or MR perfusion mismatch who were treated endovascularly demonstrated similar rates of SICH, good outcomes and mortality whether treated at < 6 hours (N=34) or > 6 hours (N=21), concluding that in appropriately selected AIS patients endovascular therapy can be performed safely regardless of stroke duration. [68] These studies imply that the therapeutic window may be protracted in selected cases and support the hypothesis that it is possible to select subjects for endovascular therapy beyond 6-8 hours TLSW using advanced multimodal neuro-imaging.

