7.5 End of the Trevo Thrombectomy Procedure (Treatment arm only)

The Trevo thrombectomy procedure should be terminated if any of the following occur:

- 1. Neurological deterioration or alteration in function is detected leading to the suspicion of an intracranial hemorrhage
- 2. The time from groin puncture reaches 2 hour
- 3. TICI grade 2b or 3 flow (reperfusion of > 2/3 MCA territory) is established
- 4. The occlusion is refractory to six retrieval attempts in a single vessel

Neurological deterioration or alteration in function leading to the suspicion of an intracranial hemorrhage will necessitate an emergent head CT or MRI scan. At the discretion of the investigator, this evaluation may also include angiography or other diagnostic tests to

Document Number: CDM10000146

determine the etiology of the clinical alteration. Management of an intracranial hemorrhage will be performed according to each institution's usual practice.

7.6 24 (-6 / +24) Hours post Randomization

The following data will be collected at 24(-6/+24) hours post randomization:

- In hospital medical management details
- NIHSS
- MRI/MRA or CT/CTA in order to assess for hemorrhage, vessel patency and infarct core volume. The same imaging modality should be used at 24 (-6/+24) hours to measure vessel patency as was used at baseline to identify occlusion location. MRI T2 Flair or CT may be used to assess core infarct volume.
- Adverse events and any treatment administered

For all subjects who expire prior to the 24 (-6/+24) hour assessment, available information regarding the primary cause of death and date/time of death will be recorded, as well as whether the subject was made "do not resuscitate" (DNR) or "comfort care only" prior to expiration.

Deaths MUST be reported to Stryker NV within 24 hours of becoming aware, preferably by CRF completion. In the event that the EDC system is unavailable a written report by e-mail or fax is acceptable.

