7.8 Day 5-7 / Discharge

The subject may be discharged from the hospital when clinically stable, at the Investigator's discretion. The following data will be collected between Day 5-7 (if subject remains in the hospital) or prior to discharge, whichever is earlier:

- In hospital medical management details
- NIHSS
- mRS (blinded assessor)
- Repeat imaging MRI T2 Flair is not required but may be performed to re-assess final core infarct volume, at the treating physician's discretion, per local practice. CT may be performed if MRI is contra-indicated. If performed, this imaging will be collected and reviewed by the Core Lab.
- Adverse events and any treatment administered
- Subject disposition

For all subjects who remain in hospital after the Day 5-7 assessments, adverse events and any treatment administered will also be recorded through Discharge. For all subjects who expire prior to the Day 5-7/Discharge assessment, available information regarding the primary cause of death and date/time of death will be recorded, as well as whether the subject was made "do not resuscitate" (DNR) or "comfort care only" prior to expiration.

Deaths MUST be reported to Stryker NV within 24 hours of becoming aware, preferably by CRF completion. In the event that the EDC system is unavailable a written report by e-mail or fax is acceptable.

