13.3 Imaging Core Labs

The independent angiographic core lab will review angiographic images from the procedure to determine revascularization and clot location.

The independent CT/MR core lab will review CT/MR images obtained at baseline and at 24 (-6/+24) hours post randomization to determine vessel patency, hemorrhage, and extent of infarcts.

Centralized imaging core labs will be used in this study to provide consistent, independent evaluation of images for confirmation of inclusion criteria. Sites will be provided with instructions for how images should be collected and submitted to Stryker NV within 2 weeks of acquisition of the final required imaging time point at 24 (-6/+24) hours after the procedure. If this timeline cannot be met for any reason, the site should communicate this delay to Stryker NV so that the pending images can be tracked until received.

Ideally MR imaging will be used whenever possible to screen subjects for inclusion into the trial. However, if MR imaging is contraindicated or is unavailable then CT based imaging may be utilized.

STRYKER CONFIDENTIAL - THIS DOCUMENT CONTAINS CONFIDENTIAL AND PROPRIETARY INFORMATION THAT IS THE PROPERTY OF STRYKER CORPORATION. NEITHER THIS DOCUMENT NOR THE INFORMATION HEREIN MAY BE REPRODUCED, USED, OR DISCLOSED TO ANY THIRD PARTY WITHOUT THE PRIOR WRITTEN CONSENT OF STRYKER CORPORATION

Document Number: CDM10000146

Ideally the same imaging modality used at baseline will be used at 24 (-6/+24) hours post randomization. However, for subjects with compromised renal function who had a CT/CTA at baseline, but in whom the treating physician wishes to avoid an additional load of contrast, an MRI/time-of-flight MRA of the intracranial arteries may be obtained instead.

An imaging core lab charter will ensure that consistent policies and procedures are applied throughout the imaging core lab review and determination process. Stryker NV is responsible for tracking images received, requesting required imaging from the sites, performing basic verification of the images received, archiving all images, transmitting and tracking images sent to the core labs, and forwarding the applicable results to the CEC.

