2.2. Secondary Objectives

To provide evidence that endovascular reperfusion with Trevo is associated with a significant reduction in median infarct size compared to the control group at 24 (-6/+24) hours post randomization.

STRYKER CONFIDENTIAL - THIS DOCUMENT CONTAINS CONFIDENTIAL AND PROPRIETARY INFORMATION THAT IS THE PROPERTY OF STRYKER CORPORATION. NEITHER THIS DOCUMENT NOR THE INFORMATION HEREIN MAY BE REPRODUCED, USED, OR DISCLOSED TO ANY THIRD PARTY WITHOUT THE PRIOR WRITTEN CONSENT OF STRYKER CORPORATION

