4.11. Estimated Duration of Subject Participation

Subjects will be followed for 90 (± 14) days post-procedure, with data collection 24(-6/+24) hours post randomization, on the day of hospital discharge or 5 to 7 days (whichever occurred sooner), 30 days (± 14 days), and 90 days (± 14 days) post-procedure. Subjects who do not withdraw prematurely from the study will be followed for a maximum of 104 days following the study procedure. Any subject who discontinues from the study for any reason will be followed to monitor safety for the duration of the study. If a subject withdraws from the study with an existing adverse event, regardless of the relationship to the study device or procedure, the subject will only be followed for a maximum of 104 days following their study procedure date.

Stryker Neurovascular

Document Title: DAWN™ Trial Statistical Analysis Plan

Document Number: CDM10000704

Rev: AB

TABLE 2. DAWN STUDY TIME AND CLINICAL ASSESSMENT SCHEDULE

Event	Screening/ Baseline	Procedure (Treatment Arm Only)	24 Hr (-6/+24) (post randomization)	Day 5-7 / Discharge (whichever is earlier)	Discharge	Day 30 ± 14	Day 90 ± 14
Inclusion/Exclusion Criteria	✓						
Demographics/Medical History/Baseline Medications	✓						
Baseline Characteristics	✓						
Baseline Labs	✓						
Informed Consent	✓						
Randomization (t=0)	✓						
Angiography Procedure Details (Treatment Arm only)		✓					
mRS [†]	✓ (pre stroke)			✓ [†]		✓ [†]	✓ [†]
NIHSS	✓ [*]		✓ ^{**}	✓		✓	✓
Neuro imaging (to assess for hemorrhage, occlusion location/vessel patency & infarct volume)***	✓ MR-DWI/MRA or CT/CTA/CTP		✓ MR-DWI/MRA or CT/CTA	✓ MR-DWI or CT (optional)			
AEs/SAEs (from time of randomization)		✓	✓	✓		✓	✓
Concomitant Medications		✓	✓	✓		✓	✓
In Hospital Med Management					✓		
Intubation Details					✓		
UB04					✓		

*NIHSS should be obtained within 1 hour of corresponding core infarct measurement.

** NIHSS should be obtained within 2 hours of the 24 (-6/+24) hour neuro-imaging to determine presence/absence of hemorrhage. [†] Must be conducted by an individual blinded to the treatment arm.

*** CT/MR and Angiographic images should be de-identified before being submitted to Stryker NV or core lab.

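### Infarct size is defined by its median but tested with an unadjusted t-test on means that ignores baseline core; this misses the stated quantity and loses some precision, without biasing the comparison

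*SAP*

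**What the plan says.** **Objective and endpoint.** SAP 2.2 and Protocol 3.2 give one secondary objective: a "significant reduction in median infarct size compared to the control group at 24 (-6/+24) hours post randomization". SAP 3.1.2 item 3 turns this into "Difference in median final infarct size at 24 (-6/+24) hours from randomization, by MRI T2/Flair or CT (if contraindicated for MR".

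**Analysis.** SAP 4.15.5 lists descriptive statistics, including the median, and a p-value from a t-test with unequal variances. The model has no covariates.

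**Timing.** Protocol 5.2.1 describes "continuous growth of the infarct core at the expense of the penumbral tissue until either the infarct is completed or reperfusion is achieved" and does not say when an unreperfused infarct is complete. Protocol 7.8 adds an optional later scan: "Repeat imaging MRI T2 Flair is not required but may be performed to re-assess final core infarct volume". The label *final* is thus attached to two time points.

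**Modality.**
- Protocol 4.2 and the synopsis follow-up schedule, SAP 3.1.2 and SAP 4.15.5: CT only where MR is contraindicated.
- Protocol 7.6: "MRI T2 Flair or CT may be used to assess core infarct volume", with no condition. Protocol 13.3.2 is also unconditional.
- Protocol 13.3: "Ideally the same imaging modality used at baseline will be used at 24 (-6/+24) hours post randomization".
- SAP Table 2, 24-hour column: "MR-DWI/MRA or CT/CTA", where the endpoint names T2/Flair.
- Protocol 5.2.6 and 13.3 accept CT at screening when MR is merely unavailable. The endpoint definition has no such case at follow-up.

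**The concern.** A test on means can disagree with a comparison of medians when volumes are skewed, so the p-value reported for the objective may not belong to the quantity the objective names. Baseline core is known before randomisation and is an obvious predictor of the later volume, so leaving it out widens the interval for no benefit.

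The scan window and the choice of CT or MRI raise a different question. Both are settled after assignment, in a trial where staff know the arm and only one arm has a procedure. If controls were scanned later, or more often by CT, part of the observed difference could come from how the infarct was measured. Stratification cannot prevent this, and the sensitivity analyses in SAP 6.2 concern missing data.

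**Working it through.** The documents give no SD, effect size or power for infarct volume, so there is no plan figure to reproduce.

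**1. Window.** 24 − 6 = 18 h and 24 + 24 = 48 h after randomisation, a width of 30 h. The entry criterion is "Subject can be randomized between 6 to 24 hours after time last known well", so scans fall between 6 + 18 = 24 h and 24 + 48 = 72 h after last known well.

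**2. Mean versus median.** Protocol Table 2 (a retrospective single-centre series) gives infarct volumes of 83.1 (64.6) and 101.2 (96.3). I assume the brackets are SDs and the unit is cc. Then 83.1 − 1.96 × 64.6 = −43.5 and 101.2 − 1.96 × 96.3 = −87.5. Volumes cannot be negative, so a symmetric normal shape does not fit and right skew is likely. Mean and median would then differ.

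**3. Precision lost by omitting baseline core.** Share of variance explained = (slope × SD of core)² / (SD of follow-up volume)², with slope assumed to be 1.
- Core uniform on 0-50 cc: SD = 50/√12 = 14.4. Share = 208.3/4173.2 = 5%.
- Largest possible SD on 0-50 cc, 25: share = 625/4173.2 = 15%.
- With the other SD in that table, 96.3: 2% and 7%.
- If the trial enriched to 0-30 cc, uniform: (900/12)/4173.2 = 1.8%.

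At 5-15%, 500 unadjusted subjects carry the information of 500 × 0.95 = 475 to 500 × 0.85 = 425 adjusted ones. These shares apply to a linear model; the gain in a median regression will differ somewhat.

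**4. Does the omission bias the test?** The planned t-test was simulated with no treatment effect: 250 per arm, 4,000 runs, two-sided 0.05. Assumed: core uniform on 0-50 cc, residual SD 40 cc, growth 1 cc/h in both arms, CT-MR offset 10 cc.

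| Scenario | Bias (treated − control) | Type I error |
|---|---|---|
| Same scan times and modality mix in both arms | 0.0 cc | 5.2% |
| Control scans 6 h later, capped at 48 h, 1 cc/h | −5.4 cc | 29% |
| The same, 0.5 cc/h | −2.8 cc | 11% |
| CT share 40% treated, 60% control | −2.1 cc | 9% |

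In the first row, adjusting for core cut the SE from 3.91 to 3.68 and left the estimate unchanged. In the other rows, adjusting for core did not remove the bias.

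**5. Does scan time alter the size of a true effect?** Assume treated growth stops 3 h after randomisation and controls grow 0.5 cc/h. If control growth lasts to 48 h, the difference is 0.5 × (18 − 3) = 7.5 cc at 18 h and 0.5 × (48 − 3) = 22.5 cc at 48 h. If control growth ends by 18 h, it is 7.5 cc throughout the window.

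**The case against.** **Starting size.** A reader might infer that ignoring baseline core mixes the treatment effect with starting size. The documents do not support that. Core is fixed before a 1:1 randomisation stratified by mismatch subgroup, whose definition includes core-volume bands (SAP 3.2). Mismatch category is also a subgroup factor (SAP 4.5), and SAP 4.4 makes an imbalanced baseline variable a potential covariate. This stands in full: the loss is precision only. The SAP 4.4 clause is conditional on imbalance, though, and does not recover that precision.

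**Growth during the scan window.** A reader might also infer that, by the protocol's own account, control infarcts are still growing when scanned. Protocol 5.2.1 gives no completion time. Its 70-80% mismatch figure refers to 9-24 h after onset, which meets the 24-72 h from last known well only at its earliest edge. The same section puts the point at which half of patients still show penumbra at 8-12 h. Continued growth is possible but not shown.

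**Scan time and modality.** Bias needs a difference between arms. Both arms share the same time zero and window, and nothing in the documents suggests a difference. If timing is equal and controls do grow on, early scans understate the benefit.

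**Modality wording.** The same-modality rule in Protocol 7.6 governs vessel patency, 13.3 states a preference, and SAP Table 2 is a visit schedule. This softens the conflict but does not remove it: CT is conditional in some sections and unconditional in others, and MR unavailability is not covered.

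**Importance.** Study success rests on mRS alone (SAP 4.2), and additional endpoint analyses are supportive without alpha control (SAP 4.5). That limits the weight of the point.

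**Conclusion.** The point holds as a mismatch between objective and test, with a modest and avoidable loss of precision. The objective and endpoint name a median; the p-value tests means. Omitting baseline core costs about 5-15% of the variance, given an SD of 64.6 from a series that was not selected like this trial, a slope of 1, and core spread across 0-50 cc. The cost is lower with the larger SD or after enrichment. The comparison remains unbiased.

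Scan time and follow-up modality are an unexamined risk, not a demonstrated bias. The figures of 9-29% for type I error illustrate what an arm difference would do under assumed growth rates and an assumed CT-MR offset; they do not predict this trial. The modality passages do conflict and need reconciling. The success criteria and interim rules are unaffected.

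**What to change.** 1. In SAP 4.15.5, make the infarct-volume analysis a median (quantile) regression on treatment arm with baseline core volume as covariate. Its coefficient is a difference in medians at a given core volume, so keep the unadjusted summary by arm alongside.
2. Report hours from randomisation to scan, and follow-up modality, by arm. Add one sensitivity analysis that accounts for both. Keep them out of the main model, because they arise after randomisation and could themselves be affected by assignment.
3. Reconcile the modality wording in Protocol 4.2, 7.6, 13.3 and 13.3.2 and in SAP 3.1.2, 4.15.5 and Table 2. State what applies when MR is unavailable but not contraindicated.
4. Describe the endpoint as infarct volume at 24 (-6/+24) h, and note that any continued growth in unreperfused subjects would make it understate the final volume.
5. Treat growth from baseline as supportive only: baseline is read on DWI or CTP-rCBF maps and follow-up on T2/Flair or CT (Protocol 13.3.2), so the difference mixes methods.

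The cost is wording plus one main model and one sensitivity model, with no new imaging, assuming scan times are captured with the images. SAP section 1 allows revision before final data lock. The label *final* would be given up.

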3.1.3. Primary Safety Outcome

Both Arms:

1. Incidence of stroke-related mortality at 90 days

3.1.4. Secondary Safety Outcome

Both Arms:

- a. Incidence of SICH, by ECASS III definition, within 24 (-6/+24) hours post randomization (time zero)
- b. Incidence of neurological deterioration from baseline NIHSS score through Day 5-7/discharge (whichever is earlier) post randomization (time zero). Neurological deterioration is defined as ≥ 4 point increase in the NIHSS score from the baseline score.

Treatment Arm:

- c. Incidence of procedure-related and device-related serious adverse events (PRSAEs and DRSAEs) through 24 (-6/+24) hours post randomization (time zero) as adjudicated by the clinical events committee, and defined as:
 - a. vascular perforation
 - b. intramural arterial dissection
 - c. embolization to a new territory
 - d. access site complication requiring surgical repair or blood transfusion
 - e. intra-procedural mortality
 - f. device failure (*in vivo* breakage)
 - g. any other complications adjudicated by the CEC to be related to the procedure

3.2. Randomization

Subjects will be randomized 1:1 to Trevo thrombectomy plus medical management or medical management alone.

Stratification will occur by: Clinical Imaging Mismatch (CIM) subgroup (see Imaging Inclusion Criteria), Time Last Seen Well (TLSW) ≥ 6 to ≤ 12 hours vs. >12 to ≤ 24 hours, and Baseline Occlusion Location (ICA vs. M1). Blocks will be assigned to all sites including the stratification mapping to maintain balance at all sites.

After randomization, no crossover is permitted.

Enrollment in this study is defined as the moment when the randomization process is completed and the subject is assigned to a study arm. In case of any protocol violations all efficacy analyses will be based on an intent-to-treat analysis where subjects are classified by the group in which they are randomized.

